For criterion (2), we will examine correlations of change in amygdala activity with change in validated self-report measures of emotional reactivity (affect, worry), and correlations of change in DLPFC activity with change in validated self-report measures of cognitive control (problem solving, dysfunctional attitudes), among Lumen and waitlist participants. A sample size of 60 will be sufficient to detect a correlation coefficient of  $r=0.4$  with 0.80 power and 2-sided  $\alpha=0.05$ . We are not focused on smaller correlations ( $r<0.4$ ) because their implications are likely to have more limited clinical relevance.

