### B. Statistical Analysis Plan

#### B.1. Treatment effects on target engagement

Based on literature and our preliminary data, we define neural targets *a priori* as activation of the amygdala for nonconscious threat-related emotion reactivity and activation of the DLPFC for cognitive control. The activation variables are from fMRI, which will be completed at weeks 0 and 16. Also, validated self-report surveys of emotional reactivity (worry, affect) and cognitive control (problem solving, dysfunctional attitudes) will be obtained at weeks 0 and 16. These self-report measures were chosen because of prior evidence for their role mediating the effect of PST on depressive symptoms.

Note that improvement for emotional reactivity corresponds to a *decrease* in amygdala activity whereas improvement for cognitive control corresponds to an *increase* in DLPFC activity. For consistency in the presentation of analyses, the measure will be constructed such that higher positive values are better; thus, change toward a *higher value is improvement*.

Activation of either neural target satisfies 2 criteria:

- i. Criterion 1. The level of task-evoked activation for either the amygdala for nonconscious threat-related emotional reactivity or for the DLPFC for cognitive control improves meaningfully from week 0 to 16 in the Lumen group compared with the waitlist control group.

The ENGAGE Phase 1 project (UIC IRB protocol #2015-1324) showed significant improvement in amygdala activation for nonconscious threat-related emotional reactivity from baseline to 2 months, and the standardized treatment effect was Cohen's  $d=0.6$ . We also underscore that the 2-month time point in that project, which tested an integrated depression and obesity behavioral treatment, coincided with the start of weight loss treatment, which was sequenced after the first 5 PST sessions for depression, so measurements of neural targets at 2 months assessed the effect of PST alone. In ENGAGE, PST was delivered via in-person individual sessions with trained coaches.

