The SPEAC project is at the frontier of research on developing a voice-based AI agent (Lumen) for PST and validating its effect on *a priori* neural targets, and the Pilot RCT (Study 1) is to estimate possible effects of target engagement, which, if promising, will support further investigation to confirm target engagement in Study 2. In this context, we apply a precision interval approach (see Section A above) to determine Criterion 1. We define that, compared with the waitlist control group, the Lumen PST treatment group will demonstrate a *meaningful improvement* in a neural target if the standardized between-group mean difference is at least Cohen's  $d=0.3$  in favor of Lumen (small effect; 50% of that in ENGAGE). At this effect size, the upper limit of the precision interval overlaps with  $d=0.8$  (large effect) given a standardized half-width of 0.5 with 90% assurance that the interval contains the true mean difference based on the power analysis. We consider such a finding to be meaningful and will suffice Criterion 1.

- ii. Criterion 2. Change in the level of task-evoked activation of a neural target that meets Criterion 1 correlates with temporally concurrent change from week 0 to 16 in self-reported measures within the corresponding PST theory-based construct for emotional reactivity or cognitive control. As noted, we consider correlations of  $r=0.4$  or greater meaningful. Specifically:
  - a. If the amygdala target exhibits a meaningful improvement in the Lumen group vs. the waitlist control (Criterion 1), then we will examine whether that improvement is significantly correlated with improvements in validated self-report measures of emotional reactivity (worry, affect) over the same 0-to-16-week interval.
  - b. If the DLPFC target exhibits a meaningful improvement in the Lumen group vs. the waitlist control (Criterion 1), then we will examine whether that improvement is significantly correlated with improvements in cognitive control (problem solving, dysfunctional attitudes) over the same 0-to-16-week interval.

Criterion 1 is tested via *t* test that compares the change from week 0 to 16 in the Lumen group with that change in the waitlist control group. Participants are analyzed based on the group to which they are assigned using all available data. The *t* test described above can be readily expanded for exploratory subgroup analyses by applying to each subgroup (e.g., female vs. male).

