To test Criterion 2, we will examine the regression change of the amygdala activity from week 0 to 16 on change in self-reported measures of emotional reactivity (worry, affect) from week 0 to 16, controlling for baseline values of the self-reported measures and group assignment. We expect that the coefficient for the change in amygdala activation is significant and positive in the direction of improvement in its corresponding, validated emotional reactivity self-report measures and that this relationship may be significantly modified by group assignment. Similarly, we will examine the regression change of the DLPFC activity from week 0 to 16 on change in self-reported measures of cognitive control (problem

solving, dysfunctional attitudes) from week 0 to 16, controlling for baseline values of the self-reported measures and group assignment. We expect that the coefficient for the change in DLPFC activation is significant and positive in the direction of improvement in its corresponding, cognitive control validated self-report measures and that this relationship may be significantly modified by group assignment.

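### The Criterion 2 regression makes activation change the outcome, then judges a coefficient for activation change that this model does not contain

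*Combined protocol and SAP*

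**What the plan says.** Section 3.0 (Aim 2) makes target engagement depend on two requirements. One is meaningful improvement in a neural target. The other is a significant correlation of change in that target with change in the matching self-report measures. Appendix 3 A ties these criteria to the transition to the R33 phase.

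For the second requirement, Appendix 3 B.1 writes: "we will examine the regression change of the amygdala activity from week 0 to 16 on change in self-reported measures of emotional reactivity", the measures being worry and affect, "controlling for baseline values of the self-reported measures and group assignment". The next sentence begins "We expect that the coefficient for the change in amygdala activation is significant and positive". The DLPFC text has the same structure, with problem solving and dysfunctional attitudes as the measures, and the same expectation: "We expect that the coefficient for the change in DLPFC activation is significant and positive". Both sentences add that the relationship may be modified by group. Section 9.0 repeats all of this almost word for word.

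Appendix 3 A gives the sample-size statement: "A sample size of 60 will be sufficient to detect a correlation coefficient of" 0.4, with 0.80 power and two-sided alpha of 0.05. Correlations of 0.4 or more are called meaningful.

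**The concern.** The regression sentence makes activation change the dependent variable. The following sentence judges a coefficient that exists only if activation change is a predictor. Both cannot hold, so an analyst has to choose.

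The regression sentence also names several measures, with their baselines, in one regression per target. Read literally, the scales enter together and each is tested net of the other. Where the plan intends one regression per predictor it says so, as in the dose analyses of Appendix 3 B.3.c. No such statement is made for Criterion 2.

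Two further points are open. The plan does not say how many scales must show the association. It also does not say whether 0.4 is a threshold to be met, or whether it refers to a raw or a partial correlation. Criterion 2 is half of the decision to proceed, so one data set could pass or fail on choices left until the data are in hand.

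**Working it through.** **Inputs.** From the documents: N = 60 (40 and 20), retention of at least 85%, r = 0.4, two-sided alpha 0.05, power 0.80. Completers: 0.85 × 60 = 51 (34 and 17). Assumed, because the documents give no figure: correlation between the scales' changes, ρ = 0.3, 0.5 or 0.7.

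**1. The plan's own figure.** By Fisher's z, n = ((1.960 + 0.842)/atanh(0.4))² + 3 = (2.802/0.4236)² + 3 = 46.7, so 47. Allowing for 15% loss, 47/0.85 is 55.3, so 56. Power is Φ(atanh(0.4)·√(n − 3) − 1.960):
- n = 60: Φ(3.198 − 1.960) = 0.89
- n = 51: Φ(2.935 − 1.960) = 0.835
- n = 51 with 2 to 5 adjusting covariates: 0.82 to 0.79

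Sixty is therefore sufficient for a single correlation of 0.4.

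**2. Does direction matter with one scale?** With the same covariates on both sides, t = r_p·√(df/(1 − r_p²)), where r_p is the partial correlation, and r_p is symmetric. On one simulated data set the slopes were 0.348 (activation on scale) and 0.258 (scale on activation), and t was 2.1555 both ways. The main-effect test is unchanged.

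**3. Does direction matter for modification by group?** Yes. Scale-change-by-group in a model for activation is a different term from activation-change-by-group in a model for the scale. On the same data, t was −0.84 and −1.88.

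**4. Two scales entered together.** If each scale's change correlates 0.4 with activation change, the partial correlation given the other scale is r_p = (0.4 − 0.4ρ)/√((1 − 0.16)(1 − ρ²)). The approximate power at n = 51 is Φ(atanh(r_p)·√(51 − 3 − 4) − 1.960), with four adjusting terms: the other scale, two baselines and group.

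| ρ | r_p | Power, formula | Power, simulation (4,000 runs) |
|---|---|---|---|
| 0.3 | 0.320 | 0.60 | 0.61 |
| 0.5 | 0.252 | 0.40 | 0.41 |
| 0.7 | 0.183 | 0.23 | 0.23 |

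The same simulation with one model per scale gives 0.84, and further runs gave 0.82 to 0.84. With all 60 retained, the joint-model figures are 0.69, 0.47 and 0.27. If PANAS contributes its positive and negative scores separately, emotional reactivity has three scores, and the joint-model power for a given score is about 0.43 to 0.1.

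**5. Any scale passing, on p < 0.05 alone.** With no association, one test passes in the favourable direction 2.5% of the time. For independent scales, 1 − 0.975² = 4.9% with two and 1 − 0.975³ = 7.3% with three. Simulation with correlated scales and separate models gives about 4 to 7% per target.

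**The case against.** The strongest reply is that only the phrasing is wrong. The coefficient sentence, the adjustment for baseline self-report and the plural correlations in Appendix 3 A all fit a model with self-report change as the outcome and activation change as the predictor. On that reading no scale is adjusted for another, and the single-scale main-effect test is what the plan intended. This is plausible. It supports the direction of the correction, but it does not make the two sentences agree.

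A reader might infer that the plan specifies a joint model. It does not say so outright; joint entry is the literal reading of one regression on several measures. Even there, a joint F test of two scales would keep power of 0.92 to 0.82 at 51 completers, but the plan describes no such test and judges a coefficient.

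A reader might infer that the stated 0.80 power is wrong. It is given for one bivariate correlation, and step 1 confirms it.

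A reader might also infer that the chance of wrongly proceeding is doubled. The 4 to 7% is for Criterion 2 alone, on p < 0.05 alone. If r ≥ 0.4 is also required, simulation puts it at about 0.5 to 0.7%. Criterion 2 is examined only for a target that has met Criterion 1. With no treatment effect, the chance of d ≥ 0.3 at 34 and 17 is about 0.16, because the standard error is √(1/34 + 1/17) = 0.297 and 0.3/0.297 = 1.01.

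Finally, the coefficient sentence is an expectation, whereas the criterion itself is worded as a significant correlation. That is true, but the sentence belongs to the paragraph that sets out how Criterion 2 is tested, and it is the only place that says which term is read.

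**Conclusion.** The contradiction is on the page, for both targets, in both Section 9.0 and Appendix 3 B.1. The Criterion 2 model cannot be run as written.

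Its effect depends on the reading. With one scale per model it changes no main-effect p value. With two scales entered together, power for a given scale at 51 completers falls from about 0.82-0.84 to about 0.6-0.2, so that model lacks the 0.80 power stated for a single correlation. These figures assume a true correlation of 0.4 for each scale, net of baseline and group, and inter-scale correlations of 0.3 to 0.7. The group-modification test depends on direction under either reading.

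The number of scales needed and the status of the 0.4 value are undefined. The documents do not support reading this as a sample-size error or as a doubled rate of false decisions to proceed.

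**What to change.** In Section 9.0 and Appendix 3 B.1, for both targets:

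- Make each scale's change from week 0 to 16 the outcome and activation change the predictor, adjusting for that scale's baseline and group, with one model per scale.
- Write the modification by group as an activation-change-by-group term.
- State, before unblinding, which scale or how many scales per target must pass.
- State whether r ≥ 0.4 is required in addition to significance, and whether it is raw or partial.

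A composite of the scales within a target may be added as a supportive analysis, but it is not the remedy. It is powerful when every scale is associated (0.89 to 0.99 in simulation). If only one scale is associated at 0.4, its power is about 0.32 to 0.40 with two scales and 0.17 to 0.23 with three, against about 0.83 for that scale's own model.

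The cost is wording only. No new data are needed and N does not change. The sponsor does have to commit in advance to a rule for the number of scales.

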### ***B.1.a. Supportive Voxelwise Whole Brain Analysis***

We will conduct an exploratory whole-brain analysis (1) to verify our *a priori* specification of neural targets, namely, amygdala for emotional reactivity and DLPFC for cognitive control, and (2) to identify any additional voxel clusters that are activated by our tasks and are associated with treatment response. This cluster-extent based thresholding analysis will be carried out using the same SPM12 software used for neuroimage processing (see the *Study 1 Protocol Synopsis*, Forms E, which contains technical details). The identification of voxel clusters employs 2 criteria: (1) a primary threshold to identify activated voxels with a test level (e.g.,  $P \leq 0.001$ ), and (2) an extent threshold applied to clusters of contiguous voxels (neighbors at 5 of 6 voxel faces activated) based on an estimated distribution of cluster sizes, to control the family-wise error rate (FWER) for clusters (e.g.,  $\alpha_{FWER} \leq 0.05$ ). Recently there has been concern that faulty statistical assumptions have led to high false-positive rates and over-large clusters that cross anatomical boundaries. We follow the recommendations of Woo et al. by setting  $P \leq 0.001$  and employing nonparametric tests that avoid problematic Gaussian random field assumptions. This specification will provide sufficient sensitivity to allow detection of alternative anatomical clusters, which we can replicate using the same analysis strategy in Study 2.

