## 1.0 Project Summary/Abstract

Depression and anxiety are the leading causes of disability and lost productivity, and are often underdiagnosed and undertreated owing to access, cost, and stigma barriers. Novel and scalable psychotherapies are urgently needed. Advances in artificial intelligence (AI) offer a transformative opportunity to develop intelligent voice assistants as virtual health agents accessible on personal devices. Meanwhile, major advances in human neuroscience have fueled a paradigm shift to study brain mechanisms underlying behavioral health interventions. Leveraging emerging science in these transdisciplinary areas, this project aims to develop and rigorously test a novel voice-enabled, AI virtual agent named Lumen, trained on Problem Solving Therapy (PST), for patients with moderate, untreated depressive and/or anxiety symptoms. The project will investigate the effect of Lumen on engagement of a priori neural targets—amygdala for emotional reactivity and dorsal lateral prefrontal cortex (DLPFC) for cognitive control—as putative mechanisms. The project has 2 phases: R61 and R33 (see Figure 1). Phase 1 is the R61 phase (years 1-2) and will be the sole focus of this protocol. Focusing on Lumen development and refinement as well as pilot testing, Phase 1 has 2 specific aims. Aim 1 on Lumen development and refinement will proceed in 2 stages: (1) scenario-based clinician evaluations, and (2) a formative user study (n=30 participants). Aim 2 is to pilot test Lumen in a 2-arm randomized clinical trial (pilot RCT), among 60 participants with moderate, untreated depression and/or anxiety who are randomized in a 2:1 ratio to receive PST with Lumen (n=40) on a secure study iPad or be on a waitlist (n=20). At weeks 0 and 16 participants will complete functional magnetic resonance imaging (fMRI) to assess neural target engagement as well as validated surveys of patient-reported outcomes (PROs) (e.g., depressive and anxiety symptoms, functioning, quality of life). In addition, participants will complete ecological daily assessments of mood, stress, appraisal and coping for 7 days every 2 weeks during the 16-week follow-up period. The Phase 1 milestones are (1) establishing the functionality, usability, and treatment fidelity of Lumen; and (2) demonstrating feasibility, acceptability, and neural target engagement. Achieving these milestones will provide the basis for the future R33 phase (Phase 2) focused on examining target engagement and PROs in a larger 3-arm RCT by comparing Lumen with a waitlist control arm and an in-person PST arm. This protocol only focuses on the R61 phase.

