corresponding, validated emotional reactivity self-report measures and that this relationship may be significantly modified by group assignment. Similarly, we examine the regression change of the DLPFC activity from week 0 to 16 on change in self-reported measures of cognitive control (problem solving, dysfunctional attitudes) from week 0 to 16, controlling for baseline values of the self-reported measures and group assignment. We expect that the coefficient for the change in DLPFC activation is significant and positive in the direction of improvement in its corresponding, cognitive control validated self-report measures and that this relationship may be significantly modified by group assignment.

In addition, we will also conduct exploratory and secondary analyses. We will conduct an exploratory whole-brain analysis (1) to verify our *a priori* specification of neural targets, namely, amygdala for emotional reactivity and DLPFC for cognitive control, and (2) to identify any additional voxel clusters that are activated by our tasks and are associated with treatment response. Secondary analyses compare differences in discrete changes in PROs from week 0 to 16 and trajectories of change based on intensive time-series ecological measures between the Lumen and waitlist control groups. Analyses of the treatment effects on PROs employ the same *t* test approach as described above for testing Criterion 1 for target engagement. Furthermore, dosing analyses are conducted within the Lumen treatment group. The primary dosing analysis examines the relationship of neural target activation in the amygdala and DLPFC to the 4 measures of dose (number and length of PST sessions, fidelity-weighted number, and length of PST sessions). The secondary dosing analysis examines the relationship of patient-report outcomes, ecological end-of-day assessments, and measures of treatment progress (e.g., PHQ9 and GAD7 across PST sessions) to the same 4 measures of dose. Given neural target activation measures and PROs are obtained at weeks 0 and 16, these analyses focus on change over the full 16-week span of the study, whereas ecological end-of-day assessments and treatment progress measures are available for a total of 8 occasions each, and thus will be considered longitudinally.

Please see Appendix 3 for detailed power analysis and statistical analysis plan.

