#### **B.4. Intention to Treat (ITT) and Handling Missing Data**

Clinical trials such as the one proposed must face the issues of dropout and missing data. We have put in place a strong plan to ensure maximum retention of participants through the course of the study, with a projected 85% or greater retention (see the *Recruitment and Retention Plan*). Data missing completely at random (MCAR) may be analyzed “as is” without imputation, as it does not introduce bias into estimates and inferences. More commonly, data are missing at random (MAR) owing to covariate-dependent events (e.g., irregular work shifts, children’s illness, transportation, and scheduling foul-ups). Our primary analysis technique, linear mixed models, is robust for MAR and provides unbiased estimates of model parameters without imputation. (One may impute as well, but the benefit is usually modestly improved power rather than changes to conclusions.) The more serious concern for behavioral interventions is the possibility that data will be missing not at random (MNAR). This occurs when dropout or missingness is related to the level of the outcome of interest (e.g., a participant’s level of depression or anxiety). If treatment is working well and symptoms of depression and anxiety have lessened, then participants may feel continuation in treatment is not necessary or beneficial. They drop out or miss sessions because the treatment seems to have worked. On the other hand, if participants experience no improvement in symptoms, they may drop out or miss sessions because they are discouraged that the treatment seems not to have worked. In either case, the loss of data is related to the outcomes under study and has the potential to bias the study’s conclusion about the intervention. Handling the problem of MNAR is difficult. First, there is no test for the presence of MNAR (*vs.* MAR). Second, there are many possible underlying sources of MNAR and there is no guarantee that explorations of missing data patterns will clearly reveal those sources. Third, missing data imputation for MNAR necessarily makes strong and untestable statistical assumptions, so that conclusions from imputed MNAR datasets must remain tentative. This picture reinforces our strong commitment to participant retention (see the Study 1 *Recruitment and Retention Plan*).

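### The whole-brain analysis is called sufficiently sensitive, but at P≤0.001 with 34 v 17 completers single-voxel power is about 1-2% for the between-group change that Criterion 1 calls meaningful

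*Combined protocol and SAP*

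**What the plan says.** Appendix 3, B.1.a gives the exploratory whole-brain analysis two purposes, which Section 9.0 repeats. One is to verify that the amygdala and DLPFC were the right targets. The other is "to identify any additional voxel clusters that are activated by our tasks and are associated with treatment response".

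The method is a voxel threshold of P≤0.001, then an extent threshold on groups of contiguous voxels "to control the family-wise error rate (FWER) for clusters", using nonparametric tests. Contiguity is described as "neighbors at 5 of 6 voxel faces activated". The section concludes: "This specification will provide sufficient sensitivity to allow detection of alternative anatomical clusters". It adds that such clusters can be replicated in Study 2 with the same strategy. It does not say whether the voxel test is one- or two-sided.

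B.1 sets the effects the plan calls meaningful: a between-group d of at least 0.3 ("small effect; 50% of that in ENGAGE") and a correlation of at least 0.4. The ENGAGE effect itself was d=0.6.

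**The concern.** A cluster-forming threshold of P≤0.001 is strict for a comparison of 40 with 20 participants, and stricter still after dropout. If the analysis can rarely detect changes of the size used in Criterion 1, the sensitivity sentence misinforms whoever reads the map. An empty map could be taken as a failure to confirm the targets, or as a sign that no other region responds. A voxel that does pass must show an observed effect well above the plausible one, so its estimate will be inflated, and surviving clusters are what Study 2 is meant to replicate.

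The contiguity rule is a separate worry. Requiring five of six face-neighbours to be active is not the usual meaning of touching voxels, and two analysts could implement it differently.

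**Working it through.** **Inputs.** Allocation is 40 v 20 (Section 1.0). Retention is at least 85% ("with a projected 85% or greater retention", B.4). Equal loss in both arms, which is an assumption, gives 0.85×40=34 and 0.85×20=17, so 51 completers and 49 degrees of freedom. The voxel threshold is 0.001 (B.1.a), taken both two- and one-sided because the plan does not say.

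**The plan's own figure.** No sensitivity figure is given for the whole-brain analysis. The nearest stated figure is the standardized half-width of 0.5 for Criterion 1. The standard error of d is approximately √(1/34+1/17)=0.297. A 90% interval has half-width t(0.95; 49)×0.297=0.498, which reproduces 0.5 if the 90% is read as coverage. The same standard error is used below.

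**Observed effect needed at a voxel.** Two-sided: 3.50×0.297=1.04. One-sided: 3.27×0.297=0.97. These are 3.5 and 3.2 times the Criterion 1 threshold of 0.3.

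**Single-voxel power for the group contrast.** Noncentral t with 49 degrees of freedom and noncentrality d/0.297:

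| True d | Two-sided | One-sided |
|---|---|---|
| 0.3 | 1.0% | 1.7% |
| 0.6 | 8.4% | 12.2% |
| 0.8 | 22.8% | 29.9% |
| 1.0 | 45.7% | 54.5% |

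Power of 80% needs d=1.30 two-sided or 1.23 one-sided. Full retention changes little: at 40 v 20, power at d=0.3 is 1.2-2.1%.

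**Correlation with response, r=0.4.** By Fisher z, two-sided, power is Φ(atanh(0.4)×√(n−3)−3.29). With n=51 this is Φ(0.4236×6.928−3.29)=36%. With n=34 (Lumen completers only) it is Φ(0.4236×5.568−3.29)=18%. Simulation gives 36% and 17%.

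**Task activation at week 0.** One-sample test, n=60, d=0.6: the critical observed d is 3.46/√60=0.447, and two-sided power is 87%.

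**Cluster level.** The documents give neither the extent of the true effect nor the smoothness, so this is an illustration under assumed values: a 40×40×40 voxel grid, FWHM of 4 voxels, ordinary face contiguity, one-sided P≤0.001, 34 v 17, 300 runs. The critical cluster size was about 52 voxels.

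| True d | 257-voxel region | 925-voxel region |
|---|---|---|
| 0.3 | 1% | 5% |
| 0.6 | 20% | 60% |
| 0.8 | 54% | 96% |

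A larger search volume would raise the critical size and lower these figures.

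**The contiguity rule, read literally in one pass on solid blocks.** It keeps 0 of 8 voxels of a 2×2×2 block, 7 of 27 of a 3×3×3, 81 of 125 of a 5×5×5, and 0 of 25 of a one-voxel-thick 5×5 sheet. Applied repeatedly until nothing changes, it removed every finite cluster tested.

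**The case against.** The best reply is that single-voxel power is the wrong measure for a cluster-extent analysis. That stands in part. At d=0.6 with a large region, the illustration gives a better than even chance of detection. A reader might infer from the voxel figures that the claim is false for every treatment-related effect, or that an empty map is the expected result whenever Lumen works. The documents do not support either. Only at d=0.3 does sensitivity stay very low on both measures.

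A second reply is that the analysis is exploratory and decides nothing. This also largely stands. Target engagement rests on Criteria 1 and 2 for the two predefined regions, and replication in Study 2 gives some protection against an inflated finding. A reader might infer that the plan would count an empty map against a target, but it contains no such rule. The risk is one of interpretation, created by pairing a verification purpose with an unsupported sensitivity claim.

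Third, it would be wrong to describe 1-8% as the power for the effects the plan calls meaningful. The d=0.6 is the earlier study's result and not a threshold, r=0.4 is also called meaningful and fares better, and sidedness is not stated.

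Fourth, the contiguity wording may be shorthand, and B.1.a refers technical details to a protocol synopsis that is not among the documents. The extent threshold removes very small clusters anyway. If the permutation null used the same rule, the critical size would shrink too, so a net loss of sensitivity has not been shown. What remains is that the literal rule erodes edges, removes thin sheets and can be implemented in more than one way.

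**Conclusion.** The sensitivity statement has no figure behind it and does not hold for between-group change of the size used in Criterion 1: power is about 1-2% per voxel and about 1-5% in the cluster illustration. At the ENGAGE effect it is 8-12% per voxel, and 20-60% by cluster for the assumed regions. For r=0.4 it is about 36% with 51 participants and 18% with 34. The statement is adequate for week 0 task activation.

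The voxel results rest on equal 15% loss in each arm and on a group contrast of change maps, which B.1.a implies but does not specify. The cluster results rest on assumed smoothness, extent and search volume. The contiguity rule needs defining, but it is not shown to cost sensitivity overall. Criteria 1 and 2 are untouched. The correction is still worth making, because it governs how the map is read and what is taken into Study 2.

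**What to change.** In Appendix 3, B.1.a:

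1. Replace the sensitivity sentence with: *Sensitivity is adequate for week 0 task activation. It is low for treatment-related change of the size called meaningful in Criterion 1 (single-voxel power about 1-2% at d=0.3; 80% needs d of about 1.2-1.3), so absence of a cluster is not evidence against a target or against other regions.*
2. Verify the a priori targets with week 0 task activation, and restrict any treatment-related check of them to the amygdala and DLPFC masks.
3. Replace the five-of-six rule with ordinary face contiguity (sharing at least one face), used identically in the observed map and the permutation null.
4. State whether the voxel test is one- or two-sided.

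The cost is SAP wording and slight extra analysis of scans already planned. The downside is a less favourable stated claim.
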